9.3 Follow-Up Activities

Follow-Up activities are as follows:

- At Day 180 post-baseline, all patients will be administered a repeat dose of AZD7442 600 mg IM or IV. The window for this treatment will be +/- 5 days from the actual due date. The dose will be administered in the same manner as the baseline dose unless patient circumstances require a different route of administration. All requirements listed above for baseline AZD7442 administration both IV and IM will be followed for the repeat dose including the one-hour post-dose observation period.
- Patients will complete follow-up Patient Experience/COA surveys on days 2, 30, 60, 90, 120, 150, 180, 181, 210, 240, 270, 300, 330 and 360 post-baseline at home. The window for these surveys will be +/- 5 days from the actual survey due date except for day 2 survey which is +5 days only.
*NB - Study participants will complete all surveys via mobile phone, desktop, laptop, tablet computer or via Call Center. The study site is not responsible for patient completion of the surveys.
- Patients will complete QoL assessments on days 2, 30, 90, 180, 270, and 360 post-baseline at home. The window for these assessments will be +/- 5 days from the actual due date except for day 2 assessment which is + 5 days only.
- Site personnel will obtain blood for serum concentration of AZD7442 at days 30, 90, 180, 270 and 360 post-baseline in the office for all patients. The window for these blood draws will be +/- 5 days from the actual due date. All

serum concentration measurements will be sent to PPD Bioanalytical Laboratory in Richmond, VA for analysis.

- Site personnel will obtain blood for RBD-IgG antibody level at days 90, 180, 270 and 360 post-baseline in the office for all patients. The window for these blood draws will be +/- 5 days from the actual due date. All RBD-IgG antibody levels will be sent to LabCorp for analysis.
- Site personnel will obtain blood for T-cell assay at Day 30 post-baseline in the office for all patients and send to Isoplexis in Branford, CT for analysis. A subset of patients will be selected including 120 patients with hematologic malignancy and 60 patients with solid tumors in order to have site personnel obtain blood for repeat T-cell assay at Day 210 post-baseline in the office and send to Isoplexis in Branford, CT for analysis. The window for these blood draws will be +/- 5 days from the actual due date.

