17.9 Clinical Outcome Measurements

All other clinical outcome measurements will be analyzed for the ITT AZD7442 600 mg IM or IV treated groups for both solid tumor and hematologic malignancy population with a Per-Protocol (PP) sensitivity analysis. These include:

- Rate of symptomatic SARS-CoV-2 infection including hospitalization and/or death
- Rate of adverse events reported by the patient or investigator across the entire study observation period
- Rate of symptoms and change from baseline in symptom severity over the observed time points. Correlation of symptom severity with log-adjusted serum concentration of AZD7442 levels, defined as the change over time from first measurement at Day 30 to Days 90, 180, 270 and 360.
- Change in log-adjusted serum concentration of AZD7442 levels, defined as the change over time from first measurement at Day 30 to Days 90, 180, 270 and 360, relative to change in clinical status for individual disease category cohorts
- Clinical treatment outcomes such as treatment discontinuation and time to treatment progression where possible
- Health care resource utilization rates for ER, urgent care, hospitalization and unplanned telehealth visits
- Rate of death will also be considered if there is sufficient information for analysis
- Factor analysis to determine which factors (e.g., age, gender, type of cancer, cancer duration, type treatment, etc.) are related to higher levels of serum concentration of AZD7442

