
Safety and Adverse Events Analyses
	
Patient safety, non-serious and serious adverse events will be determined using Patient Experience/COA survey data, physician-reported events and lab data for all qualified patients treated with either chemotherapy only, immunotherapy only, targeted therapy only, or other therapy/combination therapy only. Individual symptom severity is assessed on a 3-point scale. In this study, safety will be assessed by evaluating non-serious and serious adverse events, chest x-rays, bacterial cultures, SARS-COV-2 RNA by RT-PCR and viral genomic test results. In addition, important infectious and oncologic safety events will be reviewed from CEC-adjudicated data for symptomatic SARS-CoV-2 infection including SARS-CoV-2 related hospitalization and SARS-CoV-2 related death.
 
18.2 Available Data
 
Safety data such as physical exams, labs and ECG data that are completed during the course of routine clinical care will be available to the MediMergent medical monitor through individual patient EMR data. Collection of non-serious adverse events will be limited only to answers on the follow-up survey questions as follows: (1) related to any event that occurred in the first 24 hours post AZD7442 administration, (2) symptoms of SARS-CoV-2 infection, (3) positive PCR-RT SARS-COV-2 test, (4) any unplanned telehealth visit, (5) any non-routine office visit, and/or (6) any ER/Urgent Care visit. Such events will be documented on the nonserious adverse event form. PCR test results will be reported digitally from the testing lab to the study site and the study site will report this result to MediMergent. If the Investigator considers that there was a causal relationship between treatment with AZD7442 or protocol design/procedures and a patient’s underlying disease progression, then this must be reported as an AE or SAE.
 
For all Serious Adverse Events, a separate data collection form, based on AstraZeneca guidelines, will be completed by the study site and submitted to MediMergent for data input and analysis. All Serious Adverse Events require collection of source documentation for review by the MediMergent safety team. Reporting of Adverse Events and Serious Adverse Events will follow FDA Guidelines and AstraZeneca reporting procedures.

--	---

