25.7.5 Recording and Follow-up of AEs and SAEs

- When an AE/SAE occurs, it is the responsibility of the Investigator to review all documentation (e.g., hospital progress notes, laboratory, and diagnostics reports) related to the event. The Investigator will then record all relevant AE/SAE information. It is required for the Investigator to send photocopies or digital files of the participant's medical records to Sponsor in addition to completion of the required AE/SAE form. There may be instances when medical records for certain cases are requested by pharmacovigilance staff. In this case, all participant identifiers, with the exception of the participant number, will be redacted on the copies of the medical records before submission.
- The investigator will attempt to establish a diagnosis of the event based on signs, symptoms, and/or other clinical information. Whenever possible, the diagnosis (not the individual signs/symptoms) will be documented as the AE/SAE.
- After the initial AE/SAE report, the Investigator is required to proactively follow each participant at subsequent visits/contacts. All SAEs and non-serious AEs of special interest will be followed until the event is resolved, stabilized, otherwise explained, or the participant is lost to follow-up. Further information on follow-up procedures is given in this document.
- The Investigator is obligated to perform or arrange for the conduct of supplemental measurements and/or evaluations as medically indicated or as requested by pharmacovigilance to elucidate the nature and/or causality of the AE or SAE as fully as possible. This may include additional laboratory tests or investigations, histopathological examinations, or consultation with other health care professionals. If a participant dies during participation in the study or during a recognized follow-up period, the Investigator will provide sponsor with a copy of any post-mortem findings including histopathology. New or updated information will be recorded in the participant's medical record and submitted as supplemental information to the original report. The Investigator will submit any updated SAE data to the sponsor or designee within 24 hours of receipt of the information.

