25.8 Recording and Reporting Adverse Events

- For the purpose of processing and reporting adverse events, the study period is defined as that time period from signature of the informed consent form through the last visit of the study. AEs may be reported by the study participant (or, when appropriate, by a caregiver, surrogate, or the participant's legally authorized representative), the PI or the Study Coordinator.
- Reporting of non-serious adverse events will be limited to **ONLY** the following:
 - Any event reported by the patient on his/her follow-up survey in the first 24 hours post-administration of AZD7442
 - Any event reported by the patient on his/her follow-up survey that includes an unplanned telehealth visit, unscheduled physician office visit, ER/Urgent Care Visit
 - Any positive SARS-CoV-2 test by RT-PCR reported to the study site
 - Any symptoms of SARS-CoV-2 reported by the patient on any follow-up survey
 - If the Investigator considers that there was a causal relationship between treatment with AZD7442 or protocol design/procedures and a patient's underlying disease progression, then this must be reported as an AE or SAE.
- All AEs will be collected from baseline AZD7442 administration through day 360 post-baseline. SAEs will be collected from dose administration through the day 360 follow-up visit at the time points specified in the Schedule of Activities. However, any SAEs assessed as related to study participation (e.g., study intervention, protocol-mandated procedure, invasive tests or change in existing therapy) will be recorded from the time participant consents to participate in the study.
- Medical occurrences that begin before the start of study intervention but after obtaining Informed Consent will be recorded as Medical History/Current Medical Conditions not as AEs.
- All SAEs will be recorded and reported to the Sponsor or designee immediately and under no circumstance should this exceed 24 hours. The Investigator will submit any updated SAE data to the Sponsor or designee within 24 hours of it being available.
- Investigators are not obligated to actively seek information on AEs or SAEs after the conclusion of study participation. However, if the investigator learns of any SAE, including a death, at any time after a participant has been discharged from the study, and he/she

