25.15 Adverse Events of Special Interest

Adverse events of special interest are defined in the study protocol as relevant known toxicities as a result of signals observed from previous studies in the non-clinical programs of AZD7442. These will be updated during the course of the study based on accumulating safety data. AESI include:

- Reactions including hypersensitivity reactions occurring on same day as vaccination
- Local injection site reactions
- Coronary Ischemia
- Myocardial Infarction
- Congestive Heart Failure
- Thrombotic events-coronary, cerebral, abdominal, pulmonary or peripheral vascular

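### The closed list of reportable non-serious AEs (18.2, 25.8) contradicts the sections that require wider collection; read literally, it omits late, unattended AESIs and drug-related events

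*Protocol*

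**What the plan says.** Section 18.2 restricts non-serious AEs: "Collection of non-serious adverse events will be limited only to answers on the follow-up survey questions as follows". The categories begin "1) related to any event that occurred in the first 24 hours post AZD7442 administration, (2) symptoms of SARS-CoV-2 infection", continue with a positive RT-PCR test, and end "4) any unplanned telehealth visit, (5) any non-routine office visit, and/or (6) any ER/Urgent Care visit". Underlying disease progression that the investigator judges causally related to AZD7442 or to protocol procedures is added. Section 25.8 repeats the restriction as exclusive; its first item is "Any event reported by the patient on his/her follow-up survey in the first 24 hours post-administration of AZD7442". Neither list names the adverse events of special interest (AESIs) of 25.15 or an AE judged related to AZD7442.

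Other current text is wider. Section 17.9 plans to analyse the "Rate of adverse events reported by the patient or investigator across the entire study observation period". Section 25.7.5 says "All SAEs and non-serious AEs of special interest will be followed until the event is resolved". Section 25.7.1 has any AE after consent and dosing processed and reported, has site staff document unsolicited AEs, and names injection-site reactions as solicited survey items. Section 25.1 asks for a site form for all AEs. Section 25.8 itself also says that all AEs are collected from the baseline dose to day 360.

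On timing, 9.3 places the repeat dose at Day 180 ± 5 days and says of the surveys: "The window for these surveys will be +/- 5 days from the actual survey due date except for day 2 survey which is +5 days only". The Schedule of Activities shows Day 181 at ± 5. Section 25.15 words the hypersensitivity AESI as "Reactions including hypersensitivity reactions occurring on same day as vaccination".

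**The concern.** The two sets of rules decide which safety data exist, and no later analysis can recover an event that was not recorded. A site that works from 18.2 and the restrictive part of 25.8 will not submit a form for a late reaction that led to no visit. A site that works from 25.1 and 25.7.1 will. With up to 75 sites (6.1), this invites uneven capture.

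Two outputs depend on it: the AE rate in 17.9 and the secondary endpoint in 14.1 on the incidence of AZD7442-related side effects. If the narrow list is followed, both are understated for events of this kind.

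The Day 181 survey raises a related problem. It comes one nominal day after the redose, as the Day 2 survey does after the first dose, so it appears to be the instrument for early reactions to dose 2. Unlike Day 2, it is not prevented from being completed before the dose.

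**Working it through.** **Step 1: does the narrow list contain what the other sections need?** Take a local injection-site reaction that starts on day 3 and prompts no visit.
- 25.15: it is an AESI.
- 25.7.1: injection-site reactions are a predefined solicited AE.
- 25.7.5: as a non-serious AESI it is followed to resolution, which presupposes that it was captured.
- 18.2 and the restrictive part of 25.8: it is outside the first 24 hours, is not a COVID-19 symptom listed in 14.1, involves no RT-PCR result and no unplanned visit, and is not cancer progression. It is excluded.

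The same event is therefore required by one set of sections and shut out by the other.

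**Step 2: what still enters under the narrow list?**
- Serious AESIs, because 25.13.6 requires every SAE regardless of relationship.
- Any event that leads to an unplanned telehealth, office, ER or urgent care visit.
- Reactions that coincide with the COVID-19 symptoms of 14.1, such as fever, headache, fatigue or nausea.
- Anything in the first 24 hours after a dose.

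The gap is confined to events that are non-serious, later than 24 hours, unattended and unlike COVID-19.

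**Step 3: how long are the 24-hour windows?** Two doses × 1 day = 2 days; 2/360 = 0.6% of follow-up. This is a share of days, not of events lost.

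**Step 4: can the Day 181 survey precede dose 2?** Inputs from 9.3 and the Schedule of Activities: redose on day 180 + d and survey on day 181 + u, with d and u whole numbers from −5 to 5. There are 11 × 11 = 121 compliant pairs.
- Survey before dose: 181 + u < 180 + d, so d − u ≥ 2. A difference of k occurs in 11 − k pairs, so the count is 9 + 8 + … + 1 = 45; 45/121 = 37.2%.
- Same day: d − u = 1, 10 pairs; 10/121 = 8.3%.
- Survey after dose: 121 − 45 − 10 = 66 pairs. The longest gap is 186 − 175 = 11 days.

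If surveys are completed in order, the next one after a premature Day 181 survey is Day 210 (days 205 to 215). A premature survey needs d ≥ −3 (since u ≥ −5), which means a redose on days 177 to 185. The next survey then comes 205 − 185 = 20 to 215 − 177 = 38 days after the dose.

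**Step 5: the hypersensitivity wording.** Vaccination must be at least 14 days before baseline (8.1, 8.2), and a further dose must wait 14 days after baseline treatment (5.4). A same-day reaction to the baseline dose therefore cannot literally be a reaction on the day of vaccination. It still falls in the first-24-hour category, so what is lost is the AESI label and not the event. No comparable wait is stated for dose 2.

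**The case against.** A reader might infer that AESIs and drug-related events outside the list never reach the database. The documents do not support that. Besides the routes in step 2, medical records and claims for all patients over 12 months are obtained (9.3), all AEs go into the medical record (25.10), 25.7.1 provides for review of available records, and 18.1 draws on physician-reported events and lab data. The text is inconsistent; it does not establish certain loss.

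A thrombosis found at a routine visit and managed as an outpatient is a tempting example, but an investigator could well class it as an important medical event under 25.13.1, which makes it an SAE. A general undercount of cardiac and thrombotic risks is not shown either, because most such events would meet a seriousness criterion.

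It can also be said that the restriction is deliberate in a pragmatic study and fits the 14.1 endpoint on AE rates from survey data. That stands as a rationale, but it does not settle the conflict. Section 25.8 alone might be read as collecting widely and reporting narrowly; 18.2 closes that route by limiting collection itself.

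The same rule applies to both disease cohorts, so bias in the solid tumor versus hematologic comparison is not shown. On the survey, the questions are not in the documents, patients are observed for an hour after the redose, and the Day 210 survey could ask about earlier reactions. These points lessen the Day 181 problem but do not remove it: early reactions that begin after the observation hour could depend on recall weeks later.

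**Conclusion.** The point holds as an internal contradiction with a defined gap. Sections 18.2 and 25.8 cannot be followed together with 17.9, 25.1, 25.7.1, 25.7.5 and the all-AE sentence of 25.8. The literal list omits non-serious AESIs and investigator-judged related AEs that are late, unattended and unlike COVID-19. The likely effect is uneven capture across sites and understated absolute rates for 17.9 and for the related-side-effect endpoint of 14.1. The documents give no event rate for this residual group, so the size of the understatement cannot be stated, and the 0.6% of step 3 should not be used as a measure of it.

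The Day 181 point also holds: 45 of 121 permitted date pairs put the survey before dose 2. The 37% weights all compliant pairs equally and is a share of allowed schedules, not a forecast of missed reactions. Its relevance rests on the assumption that Day 181 is meant to capture reactions to dose 2. The 'vaccination' wording in 25.15 is editorial. Severity is moderate.

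**What to change.** 1. In 18.2 and 25.8, add two categories collected from any source (survey, investigator, records) through Day 360: every non-serious AESI of 25.15, and every AE that the investigator judges related to AZD7442. Reword 17.9, 25.1, 25.7.1, 25.7.5 and the all-AE sentence of 25.8 so that all state the same scope.
2. Tie release of the Day 181 survey to the actual date of dose 2, with a plus-only window as for Day 2. This changes the survey only and leaves the redose window as it is.
3. In 25.15, replace 'vaccination' with 'AZD7442 administration' and keep the same-day limit.

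The cost is protocol wording, one added trigger on the existing non-serious AE form and one survey-release rule in the data platform. The downside is a modest number of extra AE forms for sites.

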18.3 Reporting Guidelines

As this is a pre-approval program, safety reporting guidelines for serious adverse events are expected to be followed. In the event that a reportable safety event is identified for one or more patients, MediMergent will immediately notify AstraZeneca of such an event for their reporting purposes. The AISP will report all known safety events that would be reported in a pre-approval clinical trial on an annual basis unless otherwise requested by the FDA. SUSARs will be reported to the FDA according to 7-day or 15-day reporting guidelines.

18.4 Likely SAEs

A program including 1,500 cancer patients followed for at least 12 months would be likely to encounter one or more of the following serious adverse events: sepsis, worsening of underlying cancer, respiratory failure, worsening of COPD, CHF, and death.

18.5 Hospitalization and Deaths

For purposes of this study, all hospitalizations and/or deaths will be considered a SAE. Hospitalization for a pre-existing condition that has not worsened (i.e., change a pacemaker battery) or for elective surgery will NOT be considered a SAE unless the hospitalization is prolonged by related SARS-CoV-2 therapy complications. These events will be collected and reported as SAEs only if the event is more severe than expected for the participant's current clinical status and medical history or if the Investigator feels that it is related to study drug. These will be collected and reported as SAEs as delineated below. Since it will not be possible to delineate in a single participant whether the hospitalization is directly related to SARS-CoV-2 infection complications, their underlying cancer, treatment for this cancer or could be related to AZD7442 causing more severe disease due to ADE, all hospitalizations for management of acute illness, regardless of cause, will be sent for evaluation to the Clinical Events Committee (CEC). See Section 20.1.

18.6 Investigator Responsibilities

The Investigator and any qualified designees are responsible for detecting, documenting, and reporting events that meet the definition of an AE or SAE and remain responsible for following up AEs that are serious, considered related to the

	
study intervention or the study, or that caused the participant to discontinue the study. Data on hospitalization or death should additionally be recorded on the Safety Report Form, for all relevant sections. The method of recording, evaluating, and assessing causality of AEs and SAEs and the procedures for completing and transmitting SAE reports are provided in the Safety Reporting section of this document.
 
18.7 MediMergent Pharmacovigilance
 
The MediMergent Pharmacovigilance team will be responsible for oversight of all safety data and for determining the expectedness of all SAEs, expedited reporting of individual cases, and safety updates to regulatory authorities and AstraZeneca.

19.0 Quality of Life Data
	
19.1 Quality-of-Life Evaluations
 
All Quality-of-Life data will be derived from questions in the baseline (Day 2) and follow-up QoL assessments. Each response will be given a numeric value and the sum of all responses will serve as the QoL “score” for a given patient at a given timepoint. The scoring will be determined such that the higher the score, the better the QoL. The comparison for all patients will use a change from baseline model. Scores at each time point for all patients for a given dose and cancer type will generate a mean, SD and SEM. The change from baseline at each post-baseline timepoint will be compared using two-tailed t-test comparison with $P < .05$ as significant. The mean change from baseline will be compared for all cancer patients treated with AZD7442 600 mg IM or IV and then sub-divided by comparisons between chemotherapy only, immunotherapy only, targeted therapy only and other/combination therapy only.

20.0 Adjudication: Clinical Events Committee (CEC)
	
20.1 Clinical Events Committee Functionality
 
An independent Clinical Events Committee (CEC) will be assembled to adjudicate/evaluate using a pre-specified adjudication operations manual, all clinical events data associated with SARS-COV-2 RNA by RT-PCR positive symptomatic SARS-CoV-2 infection including SARS-CoV-2 infection relatedness and/or impact on hospitalizations and deaths. In addition, the CEC will use the available clinical

	
data to establish a standardized assessment of SARS-CoV-2 disease severity using the World Health Organization Ordinal Scale (WOS).
 
In SARS-COV-2 RNA by RT-PCR positive symptomatic SARS-CoV-2 patients, the WOS associated with the time of T-cell function blood draw will be determined by the CEC using manual review. The data to be evaluated using the patient’s electronic health record (EHR) and other available information will include the components required to determine the World Health Organization Ordinal Scale (WOS).

21.0 Data Monitoring Committee (DMC)
	
21.1 Data Monitoring Committee
 
A Data Monitoring Committee (DMC) will be established for the interim analysis. The DMC will be unblinded to therapy in this open-label study. It will oversee the study with primary responsibility for ensuring that all data meet regulatory standards for the goals and objectives of the interim analysis. Specific goals and responsibilities of the DMC include the following:
 
 • Oversight of the study with primary responsibility for review of all data generated for the interim analysis • Review of adverse event data as part of the interim analysis with special attention to the incidence of SARS-CoV-2 by RT-PCR positive patients • Conduct of the planned interim analysis including DMC recommendations relating to potential AZD7442 redosing.

22.0. Machine Learning
	
22.1 Machine Learning Application
 
Machine Learning will be applied in order to predict the incidence of SARS-CoV-2 infection based on the serum concentration of AZD7442 at Days 30, 90, 180, 270 and 360 post-baseline for solid tumor and hematologic malignancy patients.
 
Machine Learning will be used to integrate the data from Patient Experience/ COA and QoL surveys with medical records, pharmacy fill/refill and medical insurance claims data for all patients.

SUPPLEMENTAL INFORMATION

